Muscle morphology post-stroke: We collected MRI data from 17 hemiparetic subjects (6-60 months post-stroke) as well as from matched (gender, age, height and weight) controls. Individual muscle cross-sectional area (CSA) was measured in plantar flexor (soleus, med. & lat. gastroc), dorsi-flexor (tibialis anterior) and the quadriceps femoris muscle group (Figure 3). Muscle atrophy is defined as the % difference between control and hemiparetic limbs. Our data show a reduction in CSA following stroke that is muscle group dependent. Specifically, CSA was reduced in the paretic and non-paretic medial gastrocnemius (27% & 9%), lateral gastrocnemius (16% & 6%) and soleus 20% & 13%). Quadriceps muscle CSA was reduced 24% and 5% while the TA was 9% and 17% smaller in paretic and non-paretic muscle, respectively.

[figure not shown]

Figure 4: [Pi] in paretic, non-paretic and control PF muscles collected via ^{31}P -MRS showing significant differences between legs (paretic > non-paretic > control).

[figure not shown]

Figure 3: Relative differences in paretic (grey bar) and non-paretic (black bar) lower extremity muscles compared to controls. Dashed line represents average

In-vivo bioenergetics are altered and associated with muscle dysfunction post-stroke: We collected localized ^{31}P -MRS data at rest from the paretic and non-paretic limb from eight post-stroke participants as well as from the dominant limb of 8 neurologically healthy individuals matched on the basis of age, gender, height and weight. Data were acquired with a total averaging time of 5 minutes and a TR = 5 sec. Marked differences were found in resting [Pi] levels between the paretic limb and the control limb (5.43 vs. 3.01 mM Pi) as well as between the paretic and non-paretic limbs (5.43 vs. 4.46 mM Pi; Figure 4). These data demonstrate experience acquiring ^{31}P -MRS data in muscle from individuals post-stroke. In addition, the findings provide support for the contribution of *in-vivo* bioenergetics properties to be affected following stroke and negatively impact muscle function in this population.

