Summary of Experiment & Research Design: We will perform comprehensive dynamometric, electrophysiological and magnetic resonance assessments of paretic and non-paretic musculature. Measurements will be performed on a total of 28 subjects at least six months following stroke and comparisons made to the dominant leg of a group of matched (age, gender, height & weight) neurologically healthy individuals (n=28). In doing so, we will determine if, and to what extent, neural and muscular factors differ between legs (paretic vs. non-paretic vs. control). In addition, we will determine the relationship between these factors and impaired muscle power generation. Our primary outcome measures in the ankle plantar flexor and knee extensor muscle groups will include 1) peak torque and power generation determined via isokinetic and isotonic dynamometry, respectively; 2) central activation measured using superimposed neuromuscular electrical stimulation; 3) muscle cross-sectional area (CSA) determined via MRI; and 4) muscle oxidative capacity (reflected by the rate of PCr recovery) and resting concentrations of inorganic phosphate [Pi] measured using ^{31}P MR spectroscopy.

Data Analysis Plan: The influence of neural and muscular adaptations (central activation, muscle CSA, *in-vivo* oxidative capacity and [Pi]) on peak power generation at baseline will be conducted using mixed effect regression models. The mixed models will be used with random subject effects to account for the dependent nature of the data collected on paretic and non-paretic legs within the same individuals. The baseline measure of peak power generation will serve as the dependent variable, with fixed effects for leg involvement (paretic vs. non-paretic) and for neural and muscular adaptation measures. Model fit will be assessed via Akaike Information Criteria (AIC). Partial correlations and standardized β coefficients will determine those factors with the strongest influence on muscle power generation. The models will also allow us to address secondary questions such as the differences between peak power generation and neural and muscular adaptation measures in paretic and non-paretic limbs.

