Expectation: We hypothesize that the strongest predictor of impaired muscle power generation in the paretic and non-paretic legs will be central activation. Further, *in-vivo* oxidative capacity and [Pi] in both the paretic and non-paretic legs will be weakly associated with peak power generation, while CSA will only be significant in the paretic leg. We also expect significant reductions in paretic peak power generation, central activation, CSA and *in-vivo* oxidative capacity as well as an increase in [Pi], when compared to non-paretic and control legs. Further, differences in peak power, central activation and [Pi], but not CSA, will be present between the non-paretic and control legs.

Innovation: The proposed investigation combines contemporary, high resolution MR imaging and spectroscopic techniques concurrently with electrophysiological assessment of central activation impairment and dynamometric evaluations of muscle strength and power, which together will produce unequivocal evidence of the presence, magnitude and relative importance of neural and muscular factors as contributors to impaired hemiparetic muscle function.

Aim 2: Quantify the effects of POWER training on the presence and magnitude of neural and muscular adaptations in paretic and non-paretic muscle post-stroke

Rationale: To date, the physiological mechanisms that contribute to improvements in lower extremity muscle power generation in hemiparetic subjects are largely unstudied. Moreover, how these variables impact functional performance would provide a foundation for the development of effective rehabilitation interventions targeting functional recovery post-stroke.

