Data Analysis Plan: To quantify the effects of our POWER training intervention on neural and muscular adaptations, we will utilize repeated measures mixed effects regression models to assess for significant changes in our outcomes over time. Neural and muscular adaptations (on both the paretic and non-paretic legs) will serve as dependent variables in separate models, with time serving as the key independent variable in each. Various error structures associated with the repeated measures over time will be considered (e.g. compound symmetry vs. auto-regressive), and final error structures will be selected based on AIC values. Having random subject effects in the models will account for correlation among measures within subjects over time. Secondary analyses, incorporating differences in the paretic and non-paretic legs as dependent variables, will examine whether changes over time are more pronounced in the paretic vs. non-paretic leg. These models will also incorporate random subject effects to account for within-subject dependence. Error correction will be set to maintain type one error at 5% with a desired power of 80%.

Expectation: We hypothesize that POWER training will result in significant increases in muscle peak power generation, central activation, muscle CSA and in-vivo oxidative capacity as well as a concomitant decrease in [Pi]. Further, we expect changes in these variables will be greater in the paretic compared to the non-paretic leg. We also expect improvements in Clinical Assessments as a result of training as well as increases in our measures of locomotor function (see **Procedures-Specific**).

Innovation: Through conduct of the proposed experiments, we will generate a rich data set, capable of relating measures of lower extremity power generation (both in and away from the task of walking) with functional walking performance. The proposed neuromuscular assessment

[figure not shown]

Figure 13: Timeline for measures during POWER training

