Sample size determination and Statistical Approach: A total of 28 subjects will be recruited for this study. With baseline data from n=28 subjects, we will have at least 80% power to detect measures of association (i.e. partial correlations) as small as 0.5 between neural/muscular adaptations and peak power generation. Our preliminary data suggest that the intraclass correlation between measures of power on paretic and non-paretic legs is extremely high (i.e. Spearman rho = 0.81, intraclass correlation coefficient [ICC - from mixed model] ~100%). This power estimate for Aim 1 is based on 1 observation per subject; although our mixed model approach for analyses for Aim 1 will include 2 observations per subject (i.e. paretic and non-paretic leg), the detectable correlation may not be substantially lower due to the strong intraclass correlation. For Aims 2 and 3, analyses rely on longitudinal measures, and we assume (based on experience with our patient population) that no more than 15% will fail to complete all assessments. With 28 subjects enrolled and a 15% attrition rate over time (resulting in complete data on 24 subjects), we would have at least 80% power to detect changes in measures from baseline to the end of the study equivalent to 0.6 standard deviation units (i.e. effect sizes). This power estimate is based on a paired t-test framework (i.e. pre-post comparisons), and thus power is likely underestimated, since our models will also include data from mid-intervention and follow-up time periods. For example, assuming an ICC of 90% associated with within-subject responses over 4 time periods, the effective sample size (see Campbell et al., 2001) would be slightly higher (~n=26), as would be our power (~83%) to detect an effect size of 0.6. Treatment effect sizes of 0.6 are consistent with our preliminary data, in which effect sizes of 0.7 (95% CI 0.5 to 0.9), 1.5 (95% CI 1.1 to 1.9, and 0.5 (95% CI 0.1 to 1.0) were observed for improvement in gait speed, paretic leg power, and non-paretic power, respectively. With complete data on 24 subjects, we will also be able to detect whether as little as 40% of the variability in changes in gait speed can be explained by changes in the neural / muscular adaptation measures, assuming an ICC of 90% associated with within-subject responses over 4 time periods. All power estimates assume 2-sided hypothesis tests and an alpha level of 0.05 and were conducted by a biostatistician using PASS 2008 (NCSS, Kaysville, Utah).

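### The Aim 1 model gives CSA one slope shared by both legs, so it cannot test the protocol's own expectation that CSA matters only in the paretic leg

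*Combined protocol and SAP*

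**What the plan says.** Section D, Aim 1, Data Analysis Plan: baseline peak power is the dependent variable in a mixed model with random subject effects, "with fixed effects for leg involvement (paretic vs. non-paretic) and for neural and muscular adaptation measures". The measures are central activation, CSA, oxidative capacity and [Pi]. Predictors are ranked by partial correlations and standardized coefficients, and model fit is assessed by AIC. The paragraph closes: "The models will also allow us to address secondary questions such as the differences between peak power generation and neural and muscular adaptation measures", in the two limbs. No model term or test is attached to that sentence.

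Section D, Aim 1, Expectation: central activation is expected to be the strongest predictor in both legs and oxidative capacity and [Pi] weak ones in both, "while CSA will only be significant in the paretic leg".

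For comparison, the Aim 2 Data Analysis Plan takes paretic/non-paretic differences as dependent variables in secondary analyses that "will examine whether changes over time are more pronounced in the paretic vs. non-paretic leg".

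The section on sample size powers Aim 1 at 80% or more for a partial correlation of 0.5 with n=28, on one observation per subject.

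**The concern.** The expectation about CSA concerns two slopes, one per leg. The stated model has one. Run as written, it returns a single CSA estimate and a single p-value for both legs. If CSA matters only in the paretic leg, that estimate understates the paretic effect and credits the non-paretic leg with an effect it does not have. The same estimate enters the ranking of predictors.

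An analyst who notices the gap late might fit each leg separately and compare p-values. That method can show a paretic-only pattern when the slopes are in fact equal.

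**Working it through.** **1. The plan's own figure.** For r = 0.5 and n = 28, two-sided 0.05, Fisher's z gives Φ(atanh(0.5)·√25 − 1.96) = Φ(2.747 − 1.960) = 78.4%. The t-test of r gives 79.9% by simulation, and the noncentral F with fixed predictors gives 83.7%. The stated 80% is reproduced for a simple correlation. It concerns one association on one observation per subject, so it says nothing about a difference in slope between legs.

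**2. Structure.** For subject i and leg j, the stated model is

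power = a + b·leg + g1·activation + g2·CSA + g3·oxidative capacity + g4·[Pi] + u_i + e_ij.

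The CSA slope is g2 in both legs. With h·leg·CSA added (leg = 1 for paretic), it is g2 + h in the paretic leg and g2 in the non-paretic leg. The expectation concerns g2 + h, g2 and h; the stated model has only g2.

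**3. What the shared slope estimates.** Assumed inputs: true slopes 0.5 and 0, and equal residual variance in the legs. Let k be the paretic:non-paretic ratio of CSA SDs, and c the between-leg residual correlation times the between-leg CSA correlation. With known covariance,

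shared slope = 0.5(k² − ck)/(k² + 1 − 2ck).

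- k = 1: 0.5(1 − c)/(2 − 2c) = 0.25 for any c.
- k = 0.80: c = 0 gives 0.5 × 0.64/1.64 = 0.20; c = 0.81 × 0.8 = 0.648 gives 0.5 × 0.1216/0.6032 = 0.10.
- k = 0.92: c = 0 gives 0.5 × 0.8464/1.8464 = 0.23; c = 0.648 gives 0.5 × 0.2502/0.6541 = 0.19.

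The documents give no CSA SDs. The values of k come from the mean reductions under Muscle morphology post-stroke (section C), assuming equal coefficients of variation in the legs: medial gastrocnemius 0.73/0.91 = 0.80, lateral gastrocnemius 0.84/0.94 = 0.89, soleus 0.80/0.87 = 0.92, quadriceps 0.76/0.95 = 0.80.

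A REML simulation (28 subjects, two legs, four predictors, 700 replicates per setting) agrees: 0.24 to 0.26 at k = 1 and 0.12 to 0.24 for k = 0.80 to 0.92. With leg × CSA added, the mean slopes were 0.47 to 0.52 and −0.02 to 0.02.

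**4. Power of the interaction (same assumed slopes).**

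| Residual correlation | k = 1 | k = 0.80 to 0.92 |
|---|---|---|
| 0 | 37–53% | 35–53% |
| 0.5 | 50–78% | 43–74% |
| 0.81 | 78–99% | 76–98% |

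The 0.81 is the protocol's raw between-leg Spearman correlation for power, borrowed here as an assumed residual correlation. As a rough check, Fisher's z for correlations of 0.5 and 0 in independent legs gives Φ(0.5493/√(2/25) − 1.96) = 49%.

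**5. Comparing p-values from separate fits.** With equal true slopes of 0.3 to 0.5 in both legs, 10% to 27% of simulated studies showed CSA significant in the paretic leg and not in the other.

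**6. Is leg × CSA enough alone?** Assume CSA and activation correlate 0.4, activation slopes are 0.7 and 0.3 by leg, and both CSA slopes are 0.3. A shared activation slope of 0.5 leaves ±0.2 unmodelled, so the CSA slopes become about 0.3 ± 0.2 × 0.4 = 0.38 and 0.22. In two simulations the interaction was falsely significant in 8% to 16% and 10% to 20% of runs. Adding leg interactions for all four predictors brought this back to 4% to 5%, with little loss of power.

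**The case against.** **Weight.** The expectation is one clause, and Aim 1 is mainly about which factors influence power most. A slope averaged over the legs is a legitimate quantity for that ranking. This stands: a reader might infer that the whole Aim 1 analysis is invalid, and the documents do not support that.

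**Openness.** The plan speaks of models in the plural and uses AIC, so an interaction is not excluded. That is true, but neither phrase commits the plan to one.

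**The closing sentence.** A reader might infer from the contrast with Aim 2 that Aim 1 has nothing at all on differences between legs. That goes too far. The sentence on secondary questions is a vague counterpart, and the Aim 2 analysis is itself secondary and names no interaction term. But the Aim 1 sentence could mean levels or relationships, and on either reading it gives no term or test.

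**Magnitude.** The slopes, the SD ratios and the residual correlation are assumptions. With slope 0.5 and mean CSA variance fixed at 1, the paretic partial correlation at k = 0.80 is only 0.40 to 0.45, below the protocol's 0.5. Scaled to 0.5 there, power is about 56%, 76% and 98% at residual correlations of 0, 0.5 and 0.81. This also stands, so the power figures are only a guide.

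**Separate fits.** No passage proposes comparing p-values between legs. The 10% to 27% is a warning about how the gap might be filled, not a property of the plan.

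**Conclusion.** The concern holds as a structural omission: the stated Aim 1 model has no parameter that can confirm or refute a paretic-only CSA effect. That conclusion needs no numerical assumption. Its size does. With true slopes of 0.5 and 0, the shared slope is half the paretic one when CSA SDs are equal, and less than half at SD ratios of 0.80 to 0.92, which rest on equal coefficients of variation.

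The matter is confined to Aim 1 and should be fixed. A reader might extend it to the Aim 2 training analysis or the Aim 3 models, but those do not rest on this baseline model. Nor does the text forbid an interaction; it leaves one unspecified.

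**What to change.** In the Aim 1 Data Analysis Plan:

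1. Keep the common-slope model for the overall ranking if wanted, and say that it averages over the legs.
2. Prespecify a leg × CSA interaction for the stated expectation, separately for plantar flexors and knee extensors, which makes two interaction tests.
3. Report the CSA slope in each leg with its 95% confidence interval. Put CSA on one common scale for both legs, because standardizing within each leg mixes slope differences with SD differences.
4. Judge a paretic-only effect by the interaction together with both slopes, not by comparing p-values between legs. State that a non-significant non-paretic slope will not be read as no effect.
5. Fit a version with leg interactions for all four predictors, at least as a stated sensitivity analysis.

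Cost: plan wording and one added fixed effect, or four in the fuller version. Within-subject degrees of freedom are 28 − 1 − 4 − 1 = 22 with one interaction and 28 − 1 − 4 − 4 = 19 with four. The main drawback is that 28 subjects may leave the question open: under the assumed settings, the 95% interval for the non-paretic slope has a half-width of about 0.20 to 0.42.

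### Aim 1 decides which of four factors most influences muscle power by the relative size of their estimates, with no interval or test for the difference between factors, yet promises unequivocal evidence of relative importance

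*Combined protocol and SAP*

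**What the plan says.** All references are to the combined protocol and SAP.

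- **Section D, Aim 1, Data Analysis Plan.** Baseline peak power is regressed on central activation, muscle cross-sectional area (CSA), in-vivo oxidative capacity and [Pi]. The mixed model has a fixed leg effect and a random subject effect. Partial correlations and standardized betas "will determine those factors with the strongest influence on muscle power generation". AIC is named only for model fit.
- **Aim 1, Expectation.** The hypothesis is that "the strongest predictor of impaired muscle power generation in the paretic and non-paretic legs will be central activation". Oxidative capacity and [Pi] are expected to be weakly associated with power in both legs, and CSA to be significant only in the paretic leg.
- **Aim 1, Innovation.** The combined measurements "will produce unequivocal evidence of the presence, magnitude and relative importance of neural and muscular factors".
- **Sample size determination and Statistical Approach.** The plan claims "at least 80% power to detect measures of association (i.e. partial correlations) as small as 0.5" with 28 subjects. It adds: "This power estimate for Aim 1 is based on 1 observation per subject". The section notes that the model will use two legs per subject but that the second may add little, because the legs are highly correlated.

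Nowhere do the documents plan an interval for the difference between two factors, a test of that difference, or a measure of how stable the ranking is.

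**The concern.** The Expectation makes a claim about order: one factor ahead of three others. Showing that one correlation differs from zero does not establish that. An estimate can be clearly non-zero and still be indistinguishable from its neighbour. If the order is read from the size of the estimates alone, some factor comes out on top in every data set, and the report carries nothing to tell a clear lead from a chance one. This is sampling uncertainty and would remain if the four factors were uncorrelated.

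At stake is the mechanistic message. The Background (Section B) says that therapy design depends on knowing which neural and muscular characteristics matter most. A chance ordering reported as unequivocal could misdirect later work. The Aim 2 analysis of change with training is not affected.

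**Working it through.** **1. Inputs from the documents.** n = 28; two-sided alpha 0.05; four factors; partial correlation 0.5; one observation per subject for the power statement, two in the planned model; between-leg Spearman correlation of power 0.81. The true strengths of the four factors and the correlations among them are not given, so those below are assumptions.

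**2. The plan's own figure.** Using Fisher's z, power = Φ(atanh(r)·√(n − k − 3) − 1.96), where k is the number of variables partialled out.
- k = 0: atanh(0.5) = 0.549; 0.549 × √25 − 1.96 = 0.787; power 78.4%. Simulating the exact test gives about 80%.
- k = 3 (the other three factors): 0.549 × √22 − 1.96 = 0.616; power 73.1%. Simulating the exact test gives 74.8%; a fixed-predictor F-test gives 79-83% depending on convention.

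The stated 80% is therefore reproduced, nearly or fully, as a test of one association against zero. It does not concern one factor against another.

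**3. Precision of one estimate.** The 95% interval is tanh(atanh(r) ± 1.96/√(n − k − 3)). With k = 3 the half-width on the z scale is 1.96/√22 = 0.418.
- Observed 0.5: tanh(0.549 ± 0.418) = 0.13 to 0.75.
- Observed 0.3: tanh(0.310 ± 0.418) = −0.11 to 0.62.

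The two intervals overlap over most of their length.

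**4. How often the ranking misses the strongest factor.** I simulated a four-predictor regression. With uncorrelated predictors and unit residual variance, coefficient j is r_j/√(1 − r_j²); with correlated predictors it is rescaled to keep the same partial correlation. The factor with the largest absolute standardized beta or partial correlation is named; the two give nearly the same result. There were at least 6,000 trials per one-observation setting, so simulation error is at most about √(0.25/6000) = 0.6 percentage points. The two-leg version adds a leg effect and a subject effect, with variance components treated as known.

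| Assumed partial r: central activation vs the other three | Missed, one observation per subject | Missed, two legs |
|---|---|---|
| 0.5 vs 0.2, 0.2, 0.2 | 23-28% | 1-14% |
| 0.5 vs 0.3, 0.3, 0.3 | 37-41% | 8-28% |
| 0.5 vs 0.4, 0.4, 0.4 | 54-58% | 30-51% |
| 0.5 vs 0.3, 0.1, 0.1 (near the plan's expectation) | 24-27% | 3-15% |
| 0.7 vs 0.3, 0.3, 0.3 | 5-7% | not tabulated |

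The one-observation ranges cover correlations among predictors of 0 to 0.5 (0 to 0.3 in the fourth row). The two-leg ranges cover roughly 0.5 to 0.95 for the between-leg correlation of residuals and 0.3 to 0.95 for that of predictors (0.5 to 0.81 and 0.3 to 0.81 in the fourth row). Other combinations can fall a little outside.

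**5. Power for the comparison itself.** With one observation per subject and uncorrelated predictors, a formal test of central activation at 0.5 against one rival at 0.2, 0.3 or 0.4 has power of 23%, 14% or 8%.

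**The case against.** - **The planned model uses both legs.** This is the best point on the other side. The second leg helps, sometimes greatly: against rivals at 0.2 the miss rate can fall to 1%. But the gain depends on between-leg correlations of predictors and residuals that the documents do not give, and the sample size section itself warns that it may be small. If the ranking is read leg by leg, it rests on one observation per subject again. With close rivals (0.4), two legs still miss in 30-51%.
- **The plan's expectation is easier than three equal rivals.** This is fair. Under a pattern near that expectation, the miss rate is 24-27% on one observation and 3-15% on two legs. A wide lead, 0.7 against 0.3, is ranked correctly 93-95% of the time even on one observation.
- **The text may be over-read.** The analysis plan speaks of factors in the plural and does not spell out a rule based on the order of point estimates; that is an inference. The word unequivocal stands in the Innovation paragraph, not in the analysis plan. Both are true, but no other basis is offered for judging the comparative hypothesis.
- **Ranking four equal factors.** A reader might note that central activation would then come first in 25% of trials and set this against 5%. The documents do not support that comparison: 25% is one in four by symmetry at any sample size, and no passage claims a 5% error rate for the ranking.

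**Conclusion.** The concern stands in a conditional form. The comparative hypothesis of Aim 1 has no stated inference for the comparison, the power statement covers a single association, and the promise of unequivocal evidence on relative importance goes beyond what the plan can show.

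A reader might infer that 28 subjects by itself makes the ranking wrong a quarter to a half of the time. The documents do not support that. The size depends on assumed strengths and between-leg correlations: with central activation at 0.5, misses run from about 1% (two legs, rivals at 0.2) to 58% (one observation, rivals at 0.4). Nor does the reported 0.81 fix the two-leg result. It describes muscle power, not the predictors or the residuals, so no single two-leg setting can be called the best case.

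What holds across the settings tried is that the ranking is unreliable when the true strengths are close, and the planned output would not show the reader when that is so.

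**What to change.** In the Aim 1 Data Analysis Plan, add a bootstrap that resamples participants with both legs kept together and refits the model each time. Report:

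1. the difference in absolute partial correlation (or standardized beta) between central activation and each of the other three factors, with 95% intervals;
2. the share of resamples in which each factor ranks first.

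Word the conclusion on relative importance to match, for example by stating that the order is not clearly resolved when the intervals and rank shares show this. In the Innovation paragraph, drop the word unequivocal as applied to relative importance.

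I would not go further and allow the word strongest only when an interval excludes zero. In a limited simulation (400 trials of 400 resamples each), such a rule established a true lead of 0.7 against 0.3 in only about 22% of trials, whereas simple ranking is right in 93-95%. Reporting the uncertainty is enough.

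The cost is a small extra analysis on data already collected and some rewording. The downside is that the ranking will often have to be reported as uncertain.
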